Exploratory Objectives	
 
1. To compare the accuracy of Sklip System triage when used by a layperson versus near-perfect Sklip System user
 
2. To assess whether Sklip System improves triage of pigmented skin lesions of concern < 6mm in diameter as suspicious as compared to the current medical provider virtual triage method that relies on store-and-forward non-medical-device assisted smartphone clinical images
 
3. To assess whether Sklip System improves triage of thin melanomas with < 0.8 mm Breslow depth as suspicious as compared to the current medical provider virtual triage method that relies on store-and-forward non-medical-device assisted smartphone clinical images
 
4. To determine the accuracy of layperson-performed self-skin-exam(s) at-home in the identification of all suspicious pigmented skin lesions of concern present on their body as compared to the same layperson evaluated with full body skin examination by a dermatology Provider in-office
 

*Pre-specified Performance Goals	
*Pre-specified performance goals have been reviewed with the FDA for testing the Sklip System (including SMSA) as a stand-alone device.

Participant activity prior to the At-home Phase	
A copy of the Participant Mole Log Sheet (PMLS) will be provided to Participants at the beginning of the At-home Phase. All Participants will be administered a pre-survey at the start of the Study to assess baseline knowledge and comfort in performing a SSE as well as a post-survey at the end of the Study.

Blinding	
The Study Site PIs and DPs will be fully blinded to all results of the At-home Phase, including the PMLS. Participants will be informed of the blinding activity prior to their FBSE to avoid DP selection-bias. Specifically, the dermatology provider will be instructed to say the following to each participant upon entering

	
the patient room for the in-person FBSE: “Hello, my name is [name and title], the purpose of today’s visit is to complete a full body skin examination as part of the at-home dermatoscopy study. To avoid bias, please hold with any questions related to your moles of concern until I have verified that I completed your full body skin examination and all other study related activities. I will be happy to address your questions or concerns at that time.”

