--	---

	
spitz nevi, suspicion for melanoma, re-excision (or further removal) should be considered or is recommended in the pathologist management comment)
 
 
• Squamous cell carcinoma,
 
• Basal cell carcinoma
 
 
Exploratory endpoint 2:
 
Using only PSLs < 6 mm in diameter, the accuracy of the expert consensus triage decision using Participant-taken smartphone clinical images (SCI) will be assessed using a 2x2 table, where the expert consensus triage decision of “BIOPSY” or “MONITOR” will be compared to the intervention method, for both SMSA outputs recorded by Participants and SMSA outputs recorded by Study Coordinators for the same target PSLCs.
 
The Sensitivity of the SMSA output will be compared to the Sensitivity of the expert consensus triage decision of Participant-taken SCI using McNemar’s Test, given the paired nature of the data (i.e. the same PSLCs < 6mm), using 0.05 significance level.
 
The Specificity of the SMSA output will be compared to the Specificity of the expert consensus triage decision of Participant-taken SCI using McNemar’s Test using 0.05 significance level.
 
This will be done for each disease entity listed above in Exploratory endpoint 1.
 
Exploratory endpoint 3:
 
Using only Melanomas < 0.8 mm Breslow depth, the accuracy of the expert consensus triage decision using Participant-taken smartphone clinical images (SCI) will be assessed using a 2x2 table, where the expert consensus triage decision of “BIOPSY” or “MONITOR” will be compared to the intervention method, for both SMSA outputs recorded by Participants and SMSA outputs recorded by Study Coordinators for the same target PSLCs.
 
The Sensitivity of the SMSA output will be compared to the Sensitivity of the expert consensus triage decision of Participant-taken SCI using McNemar’s Test, given the paired nature of the data (i.e. the thin melanomas < 0.8 mm Breslow depth), using 0.05 significance level.
 
Exploratory endpoint 4
 
We will calculate the following based on Participant self-skin exams (SSEs) performed during the At-home Phase:
 
 
(a) the mean and standard deviation of the number of PSLCs identified by Participants performing a SSE, and
 
(b) the mean and standard deviation of the number of PSLCs identified by the dermatology Provider during the In-person Phase full body skin exam (FBSE).
 
 
The mean difference and 95% confidence interval will be calculated and assessed by paired t-test.

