4. To determine the accuracy of layperson-performed SSEs at-home in the identification of all suspicious PSLs present on their body as compared to the same layperson evaluated with full body skin examination by a dermatology Provider in-person	We will calculate the following based on Participant self-skin exams (SSEs) performed during the At-home Phase:  (a) the mean and standard deviation of the number of PSLCs identified by Participants performing a SSE, and (b) the mean and standard deviation of the number of PSLCs identified by the	First day of enrollment	Up to 42 days after first day of enrollment

	dermatology Provider during the In-person Phase full body skin exam (FBSE).		
--	---	--	--

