### 3. STUDY DESIGN

#### 3.1 DESCRIPTION OF THE STUDY DESIGN

*Refer to Section 11, Statistical Analysis for additional information regarding statistical methods used in this Study.*

All Participants of this single-arm prospective trial will be given up to 14 days to **review** the Sklip System instructions, **perform** a self-skin-exam (SSE) at-home, and **identify** PSLCs based on the following:

- (a) General concern (self or partner-identified, or non-dermatology Provider identified requiring a referral to a dermatology Provider)
- (b) Concern because the PSLC is different than the rest (i.e. “ugly duck sign”)

Then, Participants will be instructed to carefully follow provided instructions and **complete** the following for each target PSLC:

- 1) Mark the target PSLC with a green surgical marker (horizontal line) and the number (#) corresponding to the mole log, one (1) inch away from the target lesion
- 2) Record the target PSLC with a number (#) and anatomic location in the PMLS
- 3) Create a new photo album titled: “Moles” in their native smartphone/tablet Photo App
- 4) Take one (1) smartphone clinical image (SCI) of the target PSLC, twelve (12) inches away from the target skin lesion
- 5) Save the SCI in the album titled: “Moles” album
- 6) Review Sklip dermatoscope instructions for proper use
- 7) Take one (1) digital dermatoscopy image (DDI) of the target PSLC using the Sklip dermatoscope.
- 8) Save the DDI of the target PSLC in the “Moles” album
- 9) Upload the DDI to the SMSA (“Scan Moles with Ai”) within the Sklip App once per target PSLC, until either a Suspicious or Unremarkable result is obtained, for a maximum of three attempts. If after three attempts the user still receives an “Error” result, they will be prompted to document this in the participant mole log sheet.
- 10) Take one (1) screenshot of the SMSA output per target PSLC
- 11) Save the SMSA output screenshot in the album titled: “Moles”
- 12) Record each SMSA output (SUSPICIOUS, UNREMARKABLE, ERROR) in the PMLS once per target PSLC
- 13) Contact the Study Site to schedule an in-person FBSE within 28 days, if the Participant does not already have a scheduled visit

In summary, for each target PSLC the Participant will acquire the following:

One (1) smartphone clinical image (SCI)  
One (1) digital dermoscopy image (DDI)  
One (1) Sklip Mole Scanning Algorithm (SMSA) output recorded in the PMLS  
One (1) SMSA output screenshot

---

End of At-home Phase-----

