**With dermatology Provider present:**

The dermatology Provider (DP) will be blinded to the skin lesions that were selected by the study Participant at home. The DP will perform a FBSE as part of the normal clinical care pathway. All PSLCs identified by the DP as SUSPICIOUS will be marked with a vertical line one (1) inch away from the target PSLC using a green surgical marker. After completing the FBSE and marking all DP-selected suspicious PSLCs, the DP will verbally inform the Study Coordinator the Participant's Fitzpatrick skin phototype (1,2,3,4,5 or 6) after leaving the patient room.

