**Without dermatology Provider present,**

**with Study Coordinator present:**

The Participant will be asked to provide their Participant Mole Log Sheet (PMLS). Then, all PSLCs recorded in the PMLS will entered into REDCap Cloud by the Study Coordinator. Any Participant-selected PSLCs that match those identified earlier as SUSPICIOUS by the DP will be marked with a horizontal line one (1) inch away from the target PSLC using a green surgical marker. Therefore, PSLCs identified by both the DP and Participant will have a plus symbol. Next, the Study Coordinator will take and record (near-perfect) SCI and DDI for all PSLCs recorded in the PMLS and those PSLCs identified by the DP as SUSPICIOUS (not matching the Participant PSLCs). Then, the Study Coordinator will complete the following:

- 1) Take one (1) photo of the Participant identification sticker with a Study Site secure smartphone/tablet
- 2) Take one (1) smartphone clinical image (SCI) of each target PSLC recorded in the Participant Mole Log Sheet (PMLS)
- 3) Take one (1) digital dermoscopy image (DDI) of each target PSLC using the Sklip dermatoscope.
- 4) Save the DDI of the target PSLC in the Study Site smartphone/tablet native photo gallery
- 5) Upload the Study Coordinator-taken DDI to the SMSA ("Scan Moles with Ai") within the Sklip App
- 6) Take one (1) screenshot the SMSA output
- 7) Record each SMSA output (SUSPICIOUS, UNREMARKABLE, ERROR) in REDCap Cloud, per target PSLC
- 8) If the Participant has taken a set of SCI/DDI at home of a PSLC that is not intended (qualified because of anatomic body site) for the Sklip System, the Study Coordinator should still capture a set of control SCI/DDI and upload to REDCap Cloud. The Participant standard clinical care will not be changed.
- 9) If the Participant took a set of SCI/DDI of a PSLC at home but did not follow instructions – specifically uploading the DDI to the Sklip System - the Study Coordinator should remind the Participant to complete this task in the patient room (using the DDI from their mobile device gallery), upload to the Sklip System, and record the output on their Mole Log Sheet. If this situation occurs, the Study Coordinator should make a note in

REDCap Cloud; If the Participant is/was concerned about a PSLC but did not take a set of SCI/DDI at home, this PSLC will not be included in the study.

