#### *Exploratory endpoint 4*

We will calculate the following based on Participant self-skin exams (SSEs) performed during the At-home Phase:

- (a) the mean and standard deviation of the number of PSLCs identified by Participants performing a SSE, and
- (b) the mean and standard deviation of the number of PSLCs identified by the dermatology Provider during the In-person Phase full body skin exam (FBSE).

The mean difference and 95% confidence interval will be calculated and assessed by paired t-test.

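### Exploratory objective 4 asks how well self-examination finds suspicious lesions, but the planned comparison of lesion counts cannot show it

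*Combined protocol and SAP*

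**What the plan says.** The Synopsis words exploratory objective 4 as "To determine the accuracy of layperson-performed self-skin-exam(s) at-home in the identification of all suspicious pigmented skin lesions of concern present on their body", with the provider's full body examination of the same person as comparator. Section 2.2 repeats it: "To determine the accuracy of layperson-performed SSEs at-home in the identification of all suspicious PSLs present on their body".

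The endpoint column of Section 2.2 holds two summaries: "the mean and standard deviation of the number of PSLCs identified by Participants performing a SSE", and the same for the provider. The Synopsis of Statistical Analysis and Section 11.4.3 (Exploratory endpoint 4) add one sentence: "The mean difference and 95% confidence interval will be calculated and assessed by paired t-test".

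The procedures in Section 3.1 go further than the analysis. Before taking any image, the participant must "Record the target PSLC with a number (#) and anatomic location in the PMLS". At the visit, "All PSLCs identified by the DP as SUSPICIOUS will be marked with a vertical line". The coordinator then marks the overlap, so that "PSLCs identified by both the DP and Participant will have a plus symbol". Among Datasets A to L, A is the participant total, B is the provider total, and I and J hold images of provider-suspicious lesions absent from the log. No dataset records the match itself. The end-of-study survey in Section 6.1.8 asks only for the two numbers.

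**The concern.** Detection accuracy is a property of individual lesions: of those the provider calls suspicious, what share did the participant find? Two totals can agree when they refer to entirely different lesions. They can also differ when the participant found every suspicious lesion and logged others besides.

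The totals also differ in kind. Participants log lesions of general concern or that look unlike the rest, while the provider marks only those judged SUSPICIOUS. Over-selection by participants can therefore offset missed lesions and leave the counts level.

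No other section fills the gap. Sensitivity and predictive values in Section 11.4.2 concern the algorithm's output. Exploratory endpoints 1 to 3 use lesion-paired tables; endpoint 4 alone drops the pairing, although its objective also speaks of accuracy.

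At stake is whether objective 4 can be answered, and whether level counts would be misread as good detection. The Synopsis (Participant Safety) names a malignant lesion missed at self-examination as a remaining risk.

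**Working it through.** **Inputs.** Section 11.2 gives 423 lesions, 1.5 lesions per participant, 10% drop-out and 310 participants. It gives no mean number of provider-SUSPICIOUS lesions, so 0.5 to 1.5 per participant is assumed. No effect size or power is stated for endpoint 4.

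**The plan's own figure.** 1.96² × 0.974 × 0.026 / (0.10² × 0.023) = 422.98, or 423 lesions. Then 423 / 1.5 = 282 participants, and 282 × 1.10 = 310.2, or 310. This reproduces, and 282 is used below.

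**Identity.** For one participant let A be the lesions logged and B the provider's lesions.

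- A = matched + other
- B = matched + missed
- A − B = other − missed

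Matched lesions cancel. With A and B fixed, the number matched can be any integer from 0 to min(A, B), and the mean difference, its interval and the p-value do not change. Detection can then lie anywhere from 0 to Σmin(A, B) / ΣB.

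**Two constructed examples, n = 282.**

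| | Example 1 | Example 2 |
|---|---|---|
| (A, B) × participants | (2,1) × 141; (1,2) × 141 | (3,1) × 47; (2,1) × 94; (1,0) × 94; (0,0) × 47 |
| Means of A and B | 1.5 and 1.5 | 1.5 and 0.5 |
| Mean difference (95% CI) | 0.00 (−0.12 to 0.12) | 1.00 (0.93 to 1.07) |
| Paired t-test | p = 1.0 | t = 29.0, p < 0.001 |
| Detection compatible with these totals | 0/423 to 282/423, or 0% to 67% | 0/141 to 141/141, or 0% to 100% |

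**Simulation.** Here the totals vary at random: Poisson counts, participant mean 1.5, 282 participants, 1,000 simulated trials per setting, true detection set at 0%, 20%, 50%, 80% and 100%.

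| Provider mean | Mean difference across all detection levels | t-test significant |
|---|---|---|
| 1.5 | about 0.00 | about 4% to 5% at 0% to 80% detection; never at 100%, where every difference is zero |
| 1.0 | about 0.50 | 100% at every level |
| 0.5 | about 1.00 | 100% at every level |

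Only the width of the interval changed with overlap, and the plan does not use it as a measure of detection.

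**When the difference would be informative.** If the mean number of other lesions logged were known, the difference would track detection. With 0.5 others and a provider mean of 1.5, the difference is 0.5 − 1.5 × (1 − detection), which runs from −1.00 at 0% to +0.50 at 100%. The plan does not estimate that mean.

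**Precision of a lesion-level rate.** Half-width = 1.96 × √[DE × 0.7 × 0.3 / (282 × m)], with m the provider mean and DE = 1 + m × ICC (Poisson cluster sizes). Detection of 70% and ICC of 0 to 0.4 are assumed.

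| m | Provider lesions | Half-width, ICC 0 | Half-width, ICC 0.4 |
|---|---|---|---|
| 0.5 | 141 | 7.6 points | 8.3 points |
| 1.0 | 282 | 5.3 points | 6.3 points |
| 1.5 | 423 | 4.4 points | 5.5 points |

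**The case against.** - **It is a minor endpoint.** This is the last of four exploratory endpoints, with no performance goal and no role in the sample size. That is true and limits the weight of the point. It does not make the analysis answer its objective.
- **The data are nearly there.** Datasets I and J already isolate provider-suspicious lesions that were not logged, so matches might be derived as B minus J. Largely fair: the main gap is in the analysis. But the definition of Dataset B in Section 3.1 does not restrict it to SUSPICIOUS lesions (the chart-review count in Section 7.2 does), and J is described as images, not as a lesion count. A match seen only as ink on the skin may be lost.
- **The examples are built by hand.** This stands. With independent Poisson counts the intervals widen to about ±0.20 and ±0.17. The 67% ceiling belongs to that table: if A = B for everyone, 100% is possible. At 50% detection the largest half-width is 9.0 points, not 8.3. The cancellation depends on none of this.
- **The safety link is indirect.** Many provider-SUSPICIOUS lesions may be benign, so a detection rate would not measure missed malignancy directly. This also stands. The Synopsis adds that the risk belongs to ordinary self-examination and is not increased by the device.
- **The denominator is contestable.** The labelling excludes certain sites and lesion types, and participants who read it may reasonably leave such lesions unlogged. The objective, however, refers to all suspicious lesions on the body, so including them follows its wording. A stated rule would help.

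**Conclusion.** The concern holds. The planned analysis estimates a difference in counts, and that difference does not identify detection: no difference is compatible with complete failure to detect, and a highly significant one with perfect detection. This follows from algebra and needs no assumption. The numerical illustrations rest on an assumed provider mean of 0.5 to 1.5, and the precision figures also on assumed detection and within-participant correlation. The consequence is confined to objective 4. Every participant still has a provider examination, so there is no added risk to participants. The change should be made, but it is not critical to the trial's main conclusion.

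**What to change.** In the Synopsis, Section 2.2 and Section 11.4.3, make the endpoint 4 measure the lesion-level detection rate: provider-SUSPICIOUS lesions also recorded in the mole log, divided by all provider-SUSPICIOUS lesions, with a 95% confidence interval that allows for clustering within participants. The share of mole-log lesions that the provider also marked SUSPICIOUS could be added. Keep the count difference as description only.

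To support this:

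1. Add one match flag per lesion in REDCap Cloud, completed when the coordinator marks the overlap at the visit.
2. Do not derive matches as B minus J unless B is confirmed to count only SUSPICIOUS lesions and J is a complete lesion count.
3. State how a lesion that was logged but not imaged at home is counted, since Section 3.1 (coordinator item 9) leaves such lesions out of the study.
4. State whether provider-SUSPICIOUS lesions at sites or of types outside the device labelling stay in the denominator. The objective as worded includes them.

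The cost is one data field, short counting rules and a little extra analysis. Alternatively, reword objective 4 in the Synopsis and Section 2.2 as a comparison of counts and drop the claim to accuracy, which needs text changes only.

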#### 11.4.4 SAFETY ANALYSIS

Adverse events will be tabulated by the Medical Dictionary for Regulatory Activities. The severity of the AE will be assessed by National Cancer Institute (NCI) Common Terminology Criteria for Adverse Events (CTCAE) Version 5.0 criteria. Descriptive statistics using the safety evaluable population, will be used to report on all on-Study AEs, grade 3-4 AEs, treatment-related AEs, grade 3-4 treatment-related AEs, SAEs, treatment-related SAEs, and AEs

leading to discontinuation per CTCAE v5.0. Grade 3-4 laboratory abnormalities will be summarized using worst grade NCI CTCAE v 5.0 criteria.

#### 11.4.5 BASELINE DESCRIPTIVE STATISTICS

Summaries of demographics, baseline characteristics, and baseline disease characteristics will be presented for Participants will include the following:

1. Demographics: Sex (Male, Female); Age (continuous); Ethnicity; Race; Region
2. Baseline Characteristics: Height (cm); Weight (kg);

#### 11.4.6 ADDITIONAL SUB-GROUP ANALYSIS

If actual sample size will permit sub-group analysis, the analysis of the primary and secondary endpoints will be repeated but stratified by Fitzpatrick Skin Types 1—3 and 4. Additional sub-group, analysis by Site may also be performed.

### 11.5 HANDLING OF MISSING DATA

Missing data will not be imputed. Whenever possible, the analysis will be conducted using all available data. Missing data will be reported in the descriptive summary, and it will be noted if Participants were excluded from the analysis due to missing data.

## 12. CLINICAL MONITORING

### 12.1 OHSU KNIGHT CANCER INSTITUTE DATA & SAFETY MONITORING PLAN

All clinical trials at the Knight are required to have Data and Safety Monitoring Plan (DSMP). This Study is under the oversight of the Knight Cancer Institute's DSMC as described in the Knight institutional DSMP. The Knight DSMP outlines the elements required to ensure the safety of clinical trial Participants, the accuracy and integrity of the data, and the appropriate modification of cancer-related clinical trials for which significant benefits or risks have been discovered or when the clinical trial cannot be successfully concluded. The Knight DSMP also describes the methods and procedures for ensuring adequate, risk-based oversight of cancer-related research at OHSU.

As described in the Knight DSMP, regardless of a trial's risk level and any specific Knight oversight in place, the Investigator is singularly responsible for overseeing every aspect of the design, conduct, and final analysis of his/her investigation.

### 12.2 CLINICAL DATA & SAFETY MONITORING

As part of the Quality Assurance plan and in full agreement with NIH policy (NIH Guide, NIH Policy for Data and Safety Monitoring, June 10, 1998) that states all clinical trials require monitoring to ensure the safety of Study Participants and the validity and integrity of the data, monitoring will be a continuous, ongoing and multifaceted process. This includes external review by the DSMC and IRB(s), as well as internal data quality control, review and evaluation. Site monitoring visits are central to this process, and will include reporting to appropriate individuals with oversight responsibilities.

Details of monitoring activities, including designation of assigned monitoring entities, scope of monitoring visits, timing, frequency, duration of visits, and visit reporting, will be included in a separate Data and Safety Monitoring Plan (DSMP).

The Study Site Investigator is ultimately, singularly responsible for overseeing every aspect of the investigation, including design, governing conduct at all sub-Sites, and final analysis of Study data.

In the absence of a formal monitoring plan, the Investigator may work with his/her Study team to conduct and document internal monitoring of the Study to verify protection of human Participants, quality of data, and/or ongoing compliance with the protocol and applicable regulatory requirements.

If at any time Investigator noncompliance is discovered at OHSU or the satellite Study Site the corresponding Investigator shall promptly either secure compliance or end the Investigator's participation in the Study.

Independent audits will be conducted by the Knight DSMC to verify that the rights and well-being of human Participants are protected, that the reported trial data are accurate, that the conduct of the trial is in compliance with the protocol and applicable regulatory requirements, and that evidence of ongoing investigator oversight is present.

